2.5.2 Protection Against Risks

The investigators have taken multiple steps, tested in prior trials, to protect participants against potential risks of participation in a clinical trial of behavioral interventions.

In order to reduce the risk of psychological, emotional, and physical distress due to the study participation, we will make every effort to make our participants comfortable during all study procedures. Participants will be informed that they can choose not to perform any tasks or answer any question at any time, in the event that certain questions or assessment tasks cause emotional, psychological, or physical discomfort. Participants will also be encouraged to discuss any potential concerns with the research team members.

In order to minimize the risk of psychological and/or physical risks that patients with opioid-treated CLBP are more likely to experience, this study will utilize a robust safety protocol. All study personnel will be trained in this protocol.

All In-person study assessment and intervention sessions will be held at a clinical or research facility, where access to the phone will be readily available. The study interventions will be delivered in a clinical or research facility by a trained therapist with at least one other research staff member or clinician present or readily available and access to the phone readily available. When remote participation in the study activities (e.g., intervention sessions, assessment visits) is needed, the virtual delivery will take place via an approved, secure, HIPAA-compliant platform (e.g., WebEx, HIPAA-compliant Zoom, etc.) or by phone. During the in-person videorecorded activity (at baseline and exit), a researcher will walk alongside the participant for assistance; this will minimize the risk of falls. As pain flares are common in this population, participants will be encouraged to implement the study-taught techniques for pain coping and consult their regular physician, if needed, for additional pain care.

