Drs. [name], [name] (Madison, WI); [name], [name] (Boston, MA); [name], [name] (Hershey, PA) are physicians; [name] (Madison, WI) is a Nurse Practitioner; Drs. [name], [name], (Boston, MA), and [name] (Salt Lake City, UT) are clinicians practicing in the fields of mental health. All the above Investigators are experienced in the management of issues related to the treatment of CLBP and mental health problems including acute suicidality. In addition, [name] (Salt Lake City, UT) and [name] (Madison, WI) have expertise in physiotherapy for CLBP. Together, the above Investigators as well as the study therapists and other designated study clinicians will be able to address any medical or mental health issues that may arise. A designated 'on call' study physician will always be readily available via cell phone or pager for study-related questions or problems; a designated 'on call' mental health specialist will be able to address mental health related issues, including acute suicidality. A study clinician will always be consulted if the Safety Protocol is initiated (see Appendix). The Safety Protocol has been successfully utilized in the PI's prior studies. The data safety monitoring committee (DSMC) and the IRB will be timely notified in the case of a serious adverse event.

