The therapists delivering the study interventions will have a background in psychology, counseling or social work, thus well-equipped to address any potential psychological discomfort in relation to the interventions. In case of worrisome symptoms observed during the intervention sessions or assessment sessions, regardless of their mode of delivery (ie, in person, by phone, or via online platforms), the therapist or a research staff will discuss the concerns individually with the symptomatic participant, follow the Safety Protocol procedures, and contact the designated study clinician for consultation as needed if concerns persist for further assessment and directions (see Section 2.5.2 for details). Depending on clinical assessment, participants will be cleared to stay home or go home (by themselves, with family members/friends or via study-provided cab) or referred to the appropriate Emergency Department (ED). Participants who are sent home will be encouraged to contact their regular providers for evaluation, if needed, and receive a follow-up phone call the following day. Information on the resources available for counseling or other services to help with anxiety, distress, or feelings of sadness will be provided as a part of the Safety Protocol; these referred services will be paid for by the participant/participant's health plan. In case of emergency, the therapist or research staff will call 911, and the participant's emergency contact person will be notified (this procedure will be outlined in the consent/HIPAA form). Study staff will have emergency contact information available for all participants participating in a meeting.

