The additional, optional, site-specific tests will be completed for in-person study visits only. Although they are considered overall safe, should unforeseen problems occur, the main study's Safety Protocol procedures will be implemented, and the study's on-call clinician will be contacted to assess the participant. In addition, in the Salt Lake City study site, where Emotion Regulation and Cue-Reactivity (ERCR) test will be implemented, to monitor for potential risk of emotional distress, participants will be asked to rate their negative mood on a 5-point numeric rating scale (1= none, 5= extreme) before and after the ER and CR tasks, and then again at the end of the assessment session. In the unlikely event that participants report distress resulting from the task as determined by an elevation in negative mood by 2 points from baseline levels at the end of the assessment, the research staff performing the test will be trained by the PI (a licensed clinical social worker and clinician with over 12 years of experience) to debrief participants, assess risk, and provide 15 minutes of progressive muscle relaxation to ensure subjects have experienced a reduction in negative mood to a level of within 2 points of their baseline level. In three RCTs with opioid-treated chronic pain patients, [name] used the risk management strategy, and no participants remained distressed after this procedure. Should the distress level persist though, or unforeseen problems occur, the main study's Safety Protocol procedures will be implemented, and the Utah PI (a licensed clinical social worker with 12 years of clinical experience) or the study's on-call clinician will be contacted to assess the participant.

All efforts will be made to protect participant privacy and confidentiality:

- The initial screening, informed consent process and all in-person data collection will be conducted in private settings.
- During the intervention sessions, participants will be able to use their first names or nicknames, and be asked to keep the information shared by others confidential.
- During virtual study sessions, participants will be recommended to engage in the session in a private location, with headphones/earbuds if possible, and to turn off other devices as to protect confidentiality.

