11.1 Medical/Safety Monitoring

Safety protocol will be implemented by a trained researcher or therapist in case of presence of any worrisome symptoms, including inappropriate behavior during the study sessions or assessments. In case of worrisome symptoms during the intervention or assessment sessions, regardless of their mode of delivery (ie, in person, by phone, or via online platforms), a therapist or a research staff will discuss the concerns individually with the symptomatic participant, follow the Safety Protocol procedures, and call the study clinician as needed if concerns persist for further assessment and directions (see Section 2.5.2 for details). For those who are experiencing mental health problems, information on the resources available for counseling or other services to help with anxiety, distress, or feelings of sadness, will be provided. Depending on clinician's assessment, participants will be cleared to stay at home or go home (by themselves, with a family member or a friend, or via study-provided cab) or referred to the appropriate further assessment, including in the Emergency Department (ED) if needed. Participants who are excused from the assessment meeting will be asked to reschedule it; however, they will not be able to reschedule a missed intervention session. In case of emergency, the therapist or research staff will call hospital security or 911.

At each assessment session (baseline, 3, 6, 9, 12 months) participants will be screened for an intent to self-harm through their answers to item 5 on the existing outcome measure, the Current Opioid Misuse Measure (COMM): *"In the past 30 days, how often have you seriously thought about hurting yourself?"* (with responses ranging from 0=Never, 1=Seldom, 2=Sometimes, 3=Often, to 4=Very Often). Scores 3 (Often) and 4 (Very Often) will be considered a "positive screen" and trigger the research staff to initiate the Safety Protocol, which includes involving the designated study clinician for assessment of the participant's intent to harm and disposition. Depending on clinician's assessment, participants will be "cleared" or referred for appropriate further assessment, including in the Emergency Department (ED), if needed. All participants assessed by the study clinician will be provided information on the local resources available for counseling or other mental health services. COMM responses are monitored by the research staff during business hours.

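### The mood-score trigger in the optional Salt Lake City test cannot fire for participants who start at 4 or 5 on its 1-5 scale, unless the Appendix already covers them

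*Combined protocol and SAP*

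**What the plan says.** Section 2.5.2 (Protection Against Risks) describes how emotional distress is monitored during the ERCR test at Salt Lake City. Participants "rate their negative mood on a 5-point numeric rating scale (1= none, 5= extreme) before and after the ER and CR tasks", and rate it once more when the session ends. Distress due to the task is identified "as determined by an elevation in negative mood by 2 points from baseline levels at the end of the assessment". Trained staff then debrief the participant, assess risk and give 15 minutes of progressive muscle relaxation. The step is meant to ensure that the participant has had "a reduction in negative mood to a level of within 2 points of their baseline level". If distress continues, or something unforeseen happens, the main Safety Protocol applies and the Utah PI or the on-call clinician is contacted.

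Other protections surround this rule:

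- Section 2.5.2, right to decline: "Participants will be informed that they can choose not to perform any tasks or answer any question at any time".
- Section 2.5.2, general safety route: it opens "In case of worrisome symptoms observed during the intervention sessions or assessment sessions", whatever the mode of delivery.
- Section 11.1: "Safety protocol will be implemented by a trained researcher or therapist in case of presence of any worrisome symptoms".
- Section 11.1, self-harm item of the Current Opioid Misuse Measure (COMM), asked at each assessment: scores of 3 or 4 are a positive screen "and trigger the research staff to initiate the Safety Protocol, which includes involving the designated study clinician".
- Section 5.6.1: the optional test needs its own consent.

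Sections 2.5.2 and 9.2.3 refer to an Appendix for the Safety Protocol and for the details of the optional tests. That Appendix was not among the documents supplied.

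**The concern.** The trigger is a change score on a short bounded scale, and the visible text gives no criterion based on the level reached. Participants who arrive near the top of the scale have little or no room to rise, so the rule cannot select them however they react.

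A participant who goes from 4 to 5 leaves at the worst rating the scale allows, yet the score rule calls for no debrief, risk assessment or relaxation. From a start of 5 the scale cannot record any worsening. The rating is collected to watch for emotional distress, so the people whose reported distress is already highest are an awkward group for its trigger to miss. What is at stake is a participant-safety step at one optional test.

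**Working it through.** **Inputs, all from section 2.5.2.** The scale is the integers 1 to 5, with 5 the maximum. The trigger is a 2-point rise from baseline to the end of the session, read here as 2 or more. Baseline is read as the pre-task rating. The documents attach no numerical figure to this rule, so there is nothing of the plan's own to reproduce.

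**Step 1: largest possible rise.** Largest rise = 5 − start. All 5 × 5 = 25 start/end pairs can be listed.

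| Start | Largest rise | End ratings that fire now | End ratings that fire if an end rating of 5 is added |
|---|---|---|---|
| 1 | 4 | 3, 4, 5 | 3, 4, 5 |
| 2 | 3 | 4, 5 | 4, 5 |
| 3 | 2 | 5 | 5 |
| 4 | 1 | none | 5 |
| 5 | 0 | none | 5 |

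**Step 2: counts under the current rule.** Pairs that fire: 3 + 2 + 1 + 0 + 0 = 6 of 25. From starts 4 and 5: 0 of 10. Of the five pairs that end at 5, three fire (1-5, 2-5, 3-5) and two do not (4-5, 5-5).

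**Step 3: sensitivity to reading.** If the rule means a rise of exactly 2, only 1-3, 2-4 and 3-5 fire, and starts 4 and 5 still give none. If baseline means some earlier rating on the same scale, the same limit of 5 − start applies. The ceiling therefore does not depend on either choice.

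**Step 4: counts with the added criterion.** 3 + 2 + 1 + 1 + 1 = 8 of 25. The two added pairs are 4-5 and 5-5, and every starting rating now has at least one end rating that fires.

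**Step 5: the closing target.**

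- Added pairs: the rises are 1 (4-5) and 0 (5-5). Both already lie within 2 points of the start, whether that includes a difference of exactly 2 or not. The level in the current target is thus met at once, and these entries need a different closing step.
- Rise-triggered pairs: the text does not say whether a difference of exactly 2 counts as within 2 points. If it does, 1-4, 1-5 and 2-5 could close at 3, 3 and 4, each still 2 points up and so a rating that would itself fire the trigger. If within means less than 2, starts of 1, 2 and 3 close at no more than 2, 3 and 4, and the conflict disappears.

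These are counts of scale combinations. They are not frequencies of participants.

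**The case against.** The best defence is that the trigger does what it sets out to do. It looks for distress produced by the task, which is a change from baseline. A 1-point rise does not fire from any start (1-2, 2-3, 3-4 or 4-5), so 4-5 is handled like other small rises, and 5-5 shows no measured task effect at all. This stands in part: adding a level criterion is a safety policy, and for 5-5 it may pick up distress that the task did not cause. But the small rise at 4-5 is the most the scale permits, and it ends at the extreme rating, so treating it like a move from 1 to 2 is hard to defend for safety purposes.

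A second defence is that other routes exist. A reader might infer that these participants are unprotected. The documents do not support that, because staff can start the Safety Protocol on what they observe, clinicians are on call, and any task may be declined. Those routes rest on staff or participant judgement. The COMM item has a numeric cut-off but asks about self-harm thoughts over the past 30 days, so it does not measure the reaction to the images.

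A reader might also infer that 1-3, 2-4 and 3-5 satisfy the closing target the moment they fire. They do not: section 2.5.2 also requires that a reduction has taken place, and at that moment none has. Only the ambiguity about exactly 2 points remains.

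Section 2.5.2 reports that the strategy was used in three trials in opioid-treated chronic pain and left nobody distressed after the procedure. This is relevant experience, but it describes outcomes after the procedure and does not address people whom the trigger could not select.

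Finally, someone arriving at 5 would still see the images, and a check at the pre-task rating would act sooner. That is fair, but it would be a separate design choice. The change proposed here concerns only the end of the session.

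**Conclusion.** The point holds as a minor one. The mood-score rule in section 2.5.2 cannot fire from a start of 4 or 5, and this follows from the scale and the trigger alone. Whether it leaves a gap in practice depends on the Appendix, which may already deal with it. The arithmetic is therefore certain, while the procedural gap is conditional on unseen text.

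The number of participants affected cannot be estimated. Section 2.5.1 puts mild distress from the tasks at under 5% of cases. It is tempting to use the roughly 35% with elevated negative affect assumed in section 8.1 as the share starting high. That figure rests on a different instrument, the Hospital Anxiety and Depression Scale, cannot be converted to this 1-5 rating, and adds no weight here.

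The test is optional, in person only and run at one site. No endpoint, power calculation or error rate is involved.

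**What to change.** First check the Appendix. If it already covers participants who end at 5 from a start of 4 or 5, a cross-reference in section 2.5.2 is enough. Otherwise:

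- **Trigger:** a rise of 2 or more points from the pre-task rating, or an end-of-session rating of 5.
- **Closing, entries by rise:** keep the required reduction, and state that the target is a rating less than 2 points above the pre-task rating.
- **Closing, entries only under the new criterion (4-5 and 5-5):** staff complete the risk assessment, and the Utah PI or the on-call clinician is contacted if the rating stays at 5.

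The cost is two or three sentences in section 2.5.2 and the matching site procedure. The rating and the 15-minute relaxation step are already in place. The downside is a few extra debriefs and clinician contacts, some of them (5-5) for distress that the task did not cause. A 4-4 pair remains unflagged, since it shows neither a rise nor the extreme rating.

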2.5.3 Potential Benefits to Participants

Participants may experience added benefit should a given study intervention have a positive effect on their CLBP-related outcomes. All study participants can benefit from the additional safety and support net provided by the study, which may facilitate stepped-up care, if needed, more quickly than 'usual care' alone.

3 Study Objectives and Purpose

Our objective is to compare the effectiveness of MM to standard-of-care CBT for improving outcomes over a 12-month follow-up period in patients with opioid-treated CLBP.

- **Primary Objective:** To compare the effectiveness of MM to CBT, delivered in addition to "usual care," for reducing pain and increasing function (primary outcomes) in adults with opioid-treated CLBP.
- **Secondary Objective:** To compare the effectiveness of MM to CBT, delivered in addition to "usual care," for improving quality of life (QoL) and reducing daily opioid dose (secondary outcomes) in adults with opioid-treated CLBP.
- **Tertiary Objective:** To examine if participant baseline characteristics impact treatment response to MM or CBT.

4 Study Design and Endpoints

4.1 General Design

We will conduct a 5-year multi-center RCT (up to 800 participants), comparing the effectiveness of MM and CBT, delivered in addition to "usual care," for improving patient-centered outcomes in adults with opioid-treated CLBP.

Participants will be recruited by three main study sites: University of Wisconsin-Madison, Harvard University, Brigham and Women's Hospital, and University of Utah. Each participant will be followed-up for a period of 12 months. They will be randomly (1:1 ratio) assigned to MM or CBT arms; participants will receive an 8-week MM or CBT intervention, and asked to practice MM or CBT, respectively, at home daily during the entire study.

Outcome data will be collected twice virtually or in person at baseline and at exit assessment visits, and three times "remotely" (online or by phone) at 3, 6, and 9 months post-intervention start date. A subset of participants will be invited to a by-phone in-depth qualitative interview at the end of the study.

| Table 1: Timeline of Study Activities, Contact and Data Collected for Individual Participants During the 12-month Study | | | | |
|--|---|--|---|---|
| Recruitment & screening | Enrollment, Baseline Assessment, Randomization | Study Intervention | Follow-up Assessments at 3, 6 and 9 months | Exit Assessment at 12 months post-entry |
| 
 Recruitment, eligibility screen (by phone or in person) | 
 Informed consent; All survey-based data (virtually or in person) Brief videorecorded activity (virtually or in person) Randomization EHR (selected participants): prescribed opioids (researcher collected) | 
 MM/CBT course (virtually or in person; 8 weeks, 2 hours/week); MM/CBT practice (at home; entire study, 30 min/day, 6 days/week) | 
 Survey-based data (online/phone): outcome, adherence, safety data at 3, 6, and 9 months other survey data at 6 months only | 
 All survey-based data (virtually or in person); Brief videorecorded activity (virtually or in person); EHR (selected participants): prescribed opioids (researcher collected) Subgroup: in-depth interview (by phone) |

4.1.1 Primary Study Endpoints

Outcome measures are described in Section 9.2.2

- Pain intensity** will be assessed using the 0-10 point *Numerical Rating Scale* (NRS) from the Brief Pain Inventory (BPI).^{49,50}
- Physical function** will be measured using the validated *Oswestry Disability Index* (ODI);^{51,52} in addition, we will use 7 pain interference items from the BPI.^{49,50,53}

4.1.2 Secondary Study Endpoints

- Quality of life** will be assessed using the validated *Medical Outcomes Study Short Form Health Survey* (SF-12 v.2),^{54,55} a common measure of health and QoL in CLBP.⁵⁶
- Daily dose of prescription opioids** for "the past 14 days" will be collected with the *Timeline Followback* (TLFB) method,⁵⁷⁻⁵⁹ and verified against a participant's EHR data on prescribed opioids. This will enable longitudinal evaluation of opioid dose change during the proposed 52 week follow-up. To calculate a "daily opioid dose," doses of all reported opioids will be converted to a morphine-equivalent dose by multiplying daily dose of a given opioid by the published conversion factors, as we pilot-tested.⁶⁰

5 Study Participants – Enrollment and Withdrawal

We will enroll English-speaking adults with opioid-treated CLBP who are diverse in terms of gender, race, ethnicity, and mental and physical health conditions. Our sample will include participants enrolled by three sites: Madison, WI, Boston, MA, and Salt Lake City, UT.

We conservatively estimate the need to screen approximately 4,000 individuals to enroll up to 800 participants within the first 4 years, assuming the attrition rate not to exceed 20%.

5.1 Participant Population

Our sample will include participants who are patients with opioid-treated chronic low back pain, and enrolled by one of the three study sites: Madison, Wisconsin, Boston, Massachusetts, and Salt Lake City, Utah. Eligible participants will be English-speaking adults ≥ 21 years old with opioid-treated CLBP who are diverse in terms of gender, race, ethnicity, and mental and physical health conditions.

5.2 Inclusion Criteria

| Inclusion Criteria (based on self-report) |
|---|
| 1. English-speaking |
| 2. ≥ 21 years old |
| 3. Diagnosis of chronic low back pain (defined as a pain in lumbosacral region or sciatica for ≥ 3 months) as the main pain source |
| 4. Average daily pain score ≥ 3 on a 0-10 numerical rating scale (question from the Brief Pain Inventory) |
| 5. Treatment with ≥ 15 mg/day of morphine-equivalent dose for ≥ 3 months |
| 6. Report at least moderate CLBP-related disability (≥ 21 score on the Oswestry Disability Index) ⁵² |
| 7. Capable of giving informed consent |
| 8. Willing to complete all study activities |

Rationale: CLBP is the leading chronic non-cancer pain for which opioids are prescribed. Age 21 years old defines an adult per the NIH guidelines, and treatment with long-term opioids for CLBP is uncommon in those younger than 21 years.⁶¹ Because pain severity and function are the main outcomes, we will enroll those reporting at least moderate pain/disability. We will enroll patients treated with ≥ 15 mg/day of morphine-equivalent dose because: a) This dose range will enable evaluation of dose change (including any potential increases) across the spectrum of daily opioid dose categories. This is important, as the risk associated with opioid therapy is dose dependent. Even those in a lower daily dose category of 20-49 mg/day have a 44% increase in the risk of overdose compared to those treated with a daily opioid dose of less than 20 mg/day (Hazard Ratio 1.44; 95% CI: 0.57–3.62).⁶² In addition, the group of patients treated with lower daily opioid doses may have the best chance for tapering off opioids completely, should other treatments (e.g., MM) prove effective. The enrollment of patients treated with a broad spectrum of daily opioid doses will facilitate evaluation of the study intervention effects on opioid use/dose over time, especially in the proposed subgroups of participants as those treated with a lower daily opioid dose are more likely to have lower negative affect and opioid misuse scores compared to those treated with higher daily opioid doses.

